### **10.4 PAM-13**

The following PAM-13 parameters will be analyzed:

- items of scale;
- PAM 13 score;
- levels of activation.

The 13 items have four possible response options with scores from 1 to 4 (1 – strongly disagree, 2 – disagree, 3 – agree, 4 – strongly agree) and an additional “not applicable” option.

PAM 13 score is a value on scale from 0 to 100. This score will be converted to one of the four levels of activation:

- disengaged and overwhelmed (1);
- becoming aware, but still struggling (2);
- taking action (3);
- maintaining behaviors and pushing further (4).

The PAM 13 score and the level of activation will be obtained using Excel file “PAM 13 Scoring Spreadsheet 2015.xlsm” which was received from the Sponsor’s company.

In case of missing item values, the value for replacement will be determined as the integer part of the available items mean value (i.e. worst-case value imputation).

However, if there are less than ten items answered, no summary score will be calculated (the answers of this patient will be reported only in tables with descriptive statistics for items of scales).

Summary tables for the PAM 13 score will show descriptive statistics for time point values and changes from baseline value. Summary tables for the levels of activation will show descriptive statistics for time point values.

---

 Parameter “Will patient participate / or is patient participating in the AbbVie patient support program (PSP)?” from eCRF form “DEMOGRAPHICS”.

In addition the models of analysis of covariance (ANCOVA) will be applied for EoT time point to investigate the effect of the different ABBVIE REGIMENS ( $\pm$  RBV and duration) on the PAM 13 score using the corresponding baseline value as covariates.

The PAM 13 result for EoT time point will be used as dependent variable. Treatment regimen group will be used as factor. Baseline values will be used as covariates. Independent-samples t-test will be used for post-hoc comparisons. If there are more than two treatment groups, the no adjustment will be used to counteract the problem of multiple comparisons due to explanatory study nature. The obtained p-values of significance levels will be presented before and after the application of the correction.

ANCOVA results will be prepared using SAS PROC MIXED. Studentized residuals figures will be presented for each ANCOVA analyses.

As a supporting analysis the comparisons using Mann-Whitney U-test will be performed.

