9.7.6 PSP and PAM

The contribution of the patient support program (PSP) to disease control, treatment continuation over time, patient satisfaction and PSP utilization will be analyzed using descriptive and exploratory statistical methods. Appropriate frequency tables will summarize all corresponding variables of the PSP questionnaire (see ANNEX 4 and 5) over time stratified by ABBVIE REGIMEN arms. In addition, multiple logistic regression (MLR) analysis will be performed to investigate the association between the use of the PSP and the patient satisfaction variables of the PSP questionnaire with the probability of treatment completion. These MLRs will be performed similar to the MLRs for SVR12 (see Section 9.7.3.3. Additional details will be specified in the SAP).

The Patient Activation Measure (PAM) 13 item scale is a measure used to assess the patient knowledge, skill, and confidence for self-management. Each of the 13 items can be answered with one of four possible response options, which are “disagree strongly” (1), “disagree” (2), “agree” (3), “agree strongly” (4).

Based on responses to the 13-item measure, the score is calculated by adding up the raw scores (range of the sum: 13 – 52) and mapping up the value onto a scale of 0–100 indicating strength of agreement with the 13 items $(100 * (\text{sum} - 13) / (52 - 13))$. The final score can be assigned to one of the four levels of activation. A higher score indicates that the patient is likely to participate more actively in health care processes and takes more responsibility for his or her health.

In case of missing item values, the mean value of the available items will be used for replacement. However, if there are less than nine items answered, no summary score will be calculated.

A summary table will show descriptive statistics (n, mean, median, SD, minimum and maximum) for the summary score at baseline and the post-baseline time points, as well as changes from baseline. In addition analysis of covariance (ANCOVA) will be applied to investigate the effect of the different ABBVIE REGIMENS (\pm RBV and duration) on the

Confidential Information

No use or disclose outside AbbVie is permitted without prior written authorization from AbbVie
Version 3.0 (22 Apr 2015) – country v 1.0 dated 26.06.2015 Page 39 of 61

summary score using the corresponding baseline value as covariates. Further details will be specified in the SAP.

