### **16 Summary of changes to the Protocol**

The analyses methods in this SAP is fully consistent with the clinical study Protocol. The MLR analysis for the PSP results will not be performed due to lack of main predictor variability (the fact of the PSP usage is always “Yes”).

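### SAP 10.4 fills missing PAM-13 items with a truncated mean, which lowers almost every affected score (by at most 6.9 points on the protocol's scale), and its minimum number of answered items differs from the supplied protocol

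*SAP*

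**What the plan says.** Protocol 9.7.6 (version 3.0) scores each of the 13 items from 1 to 4, adds them to a sum between 13 and 52, and maps the sum linearly to 0–100. On missing items it states: "In case of missing item values, the mean value of the available items will be used for replacement". It also sets a floor: "if there are less than nine items answered, no summary score will be calculated".

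SAP 10.4 gives a different replacement rule, namely that "the value for replacement will be determined as the integer part of the available items mean value", and labels it a worst-case imputation. Its floor differs too: "if there are less than ten items answered, no summary score will be calculated". The score and the activation level come from a sponsor-supplied Excel spreadsheet; the SAP does not write out the conversion to 0–100.

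SAP 16 states: "The analyses methods in this SAP is fully consistent with the clinical study Protocol". The only change it then lists is the dropped multiple logistic regression for the patient support program. SAP 2 names protocol version 4.0 of 11 July 2017 as its basis. The protocol to hand is version 3.0 of 22 April 2015.

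**The concern.** The integer part of a mean is never above the mean. A patient whose answered items average 3.9 is credited with 3 for each unanswered one. The loss depends on the decimal part of that average and on how many items are blank, neither of which has anything to do with activation.

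The resulting score feeds the PAM-13 summaries, the change from baseline, the activation levels and the end-of-treatment ANCOVA by regimen. If item non-response differed between visits or between regimens, part of any apparent change or difference would come from the imputation rule.

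The label is also wrong. The lowest item value is 1, so a true worst case would impute 1. The SAP rule is neither that nor neutral.

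**Working it through.** **Inputs.** Thirteen items scored 1–4 (both documents). Score = 100 × (sum − 13)/39 (Protocol 9.7.6). Replacement value for a blank item: the mean m of the answered items (protocol), or floor(m) (SAP). Minimum answered: 9 (protocol version 3.0), or 10 (SAP).

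**Protocol scale reproduced.** All items at 1 give sum 13 and score 0; all at 4 give sum 52 and score 100, as stated.

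**Shortfall for one patient.** With k items missing, protocol score minus SAP score = 100 × k × (m − floor(m))/39. This is never negative.

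**Largest shortfall.** With 13 − k answered items, the largest possible decimal part is (12 − k)/(13 − k).

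- k = 1: 100 × 1 × (11/12)/39 = 2.35
- k = 2: 100 × 2 × (10/11)/39 = 4.66
- k = 3: 100 × 3 × (9/10)/39 = 6.92

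**Average over all possible sums.** With n = 13 − k answered items there are 3n + 1 possible sums. Each decimal part 0/n to (n − 1)/n occurs three times, plus one further zero at the top, so the mean decimal part is 3(n − 1)/[2(3n + 1)].

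- k = 1: 33/74 = 0.446; 100 × 1 × 0.446/39 = 1.14
- k = 2: 30/68 = 0.441; 100 × 2 × 0.441/39 = 2.26
- k = 3: 27/62 = 0.435; 100 × 3 × 0.435/39 = 3.35

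The shortfall is zero for only 4 of 37, 4 of 34 and 4 of 31 possible sums. These averages are unweighted; real sums are not equally likely.

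**Against complete data.** The check simulated 100,000 patients per setting, with independent items, three assumed answer distributions and items missing at random. The protocol rule had a bias of at most 0.03 points in size. The SAP rule had:

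| Missing items | Bias under the SAP rule (points) |
|---|---|
| 1 | −1.0 to −1.4 |
| 2 | −2.0 to −2.7 |
| 3 | −3.0 to −3.9 |

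**Worked example.** Ten answers summing to 39, so m = 3.9.

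- Protocol: sum 39 + 3 × 3.9 = 50.7; score 100 × 37.7/39 = 96.7
- SAP: sum 39 + 3 × 3 = 48; score 100 × 35/39 = 89.7
- True worst case: sum 39 + 3 × 1 = 42; score 100 × 29/39 = 74.4

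**The minimum.** A patient with exactly nine answers is scored under protocol version 3.0 and not under the SAP. If truncation were applied with four items missing, the largest shortfall would be 100 × 4 × (8/9)/39 = 9.12. The ten-item minimum therefore caps the loss at 6.92.

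**The case against.** The other side has several fair points, and most of them limit the size of the problem.

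- **Protocol version.** The SAP's consistency statement refers to version 4.0. If that version already carries the SAP's rules, nothing is undisclosed. A reader might infer that SAP 16 conceals two departures; the documents show only that both rules differ from version 3.0. This stands, but it does not remove the effect of truncation.
- **The ten-item minimum.** A reader might infer that it also pulls scores down. It does not: it changes who is scored and, as shown, limits the truncation loss.
- **Size.** The 6.92 points are a maximum on a linear mapping that the spreadsheet may not use. For a group mean the effect is diluted: if 5–30% of patients missed one item (an assumption; no rate is given), the average shift would be 0.05 × 1.14 = 0.06 to 0.30 × 1.14 = 0.34 points.
- **Frequency.** It is tempting to argue that N/A answers will make missing items common. Neither document says that N/A counts as missing. Protocol Annex 3 gives it its own code, and the shell of SAP Table 3.12.1 shows it as a response category.
- **Change and comparisons.** Similar missingness at both visits largely cancels, and nothing in the documents suggests that item non-response differs by regimen. Distortion of change or of the ANCOVA is possible, not shown.
- **Whole-number input.** The spreadsheet may accept only integers. The SAP does not say so, and that need would not justify always rounding down.
- **Importance.** The rule is prespecified and reproducible, and the instrument is secondary. This bears on priority, not on whether the rule is sound.

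**Conclusion.** The point holds in a limited form. As written, the SAP rule never raises and almost always lowers a PAM-13 score that has missing items. On the protocol's linear scale the loss is at most 2.35, 4.66 and 6.92 points for 1, 2 and 3 missing items, and about 1.1, 2.3 and 3.4 points on average over possible sums. Bias here means relative to the protocol rule, or to the complete-data score if items are missing at random. The direction carries over to the spreadsheet if its conversion is monotone; the point sizes may not. The cut-points for the activation levels are not given, so the effect on levels cannot be sized.

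The nine-versus-ten difference is a separate inconsistency about who is scored. Both differences are absent from SAP 16 when read against version 3.0; whether they are departures from version 4.0 cannot be settled here. The impact is confined to a secondary, exploratory questionnaire and to patients with missing items. SVR12 is unaffected, so this is a low-priority correction.

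**What to change.** In SAP 10.4:

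1. Replace missing items with the untruncated mean of the answered items. If the spreadsheet does not accept non-integer entries, use its own missing-item rule, without truncation. Drop the worst-case label.
2. Align the minimum number of answered items with the protocol version in force (nine in version 3.0).
3. State whether N/A counts as missing or as answered, since this decides how often the rule applies.

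In SAP 16, list any difference from the protocol that remains.

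The cost is a few sentences in the SAP and, if the spreadsheet takes non-integers, about one line of code. Two checks come first: the PAM-13 rule in protocol version 4.0, and how the spreadsheet handles missing or non-integer entries. No new data are needed.

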## 11 Safety analysis

Safety analysis will be conducted on *the safety population (SP)*. The results will be reported overall and for scheduled treatment combination ( $\pm$  RBV) and duration (12 or 24 weeks) groups.

The following parameters will be analyzed:

- study drug exposure;
- adverse events;
- pregnancies;
- clinical laboratory evaluations.

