analysis groups. Response rates (i.e. SVR12 rate, end of treatment [EoT] response rate, relapse rate, viral breakthrough) will be determined for the various CP analysis groups. The relapse rates will be estimated in patients of the CP analysis groups with EoT response and sufficient HCV RNA measurements post treatment. Viral breakthrough rates will be estimated in all patients of the CP analysis groups, who have at least one undetectable HCV RNA measurement on treatment and at least one on-treatment or EoT measurement thereafter. For all rates specified above 95%-confidence intervals (CIs) will be determined using the Clopper-Pearson method.

Univariate and multiple logistic regression (MLR) methods will be used to investigate the impact of various explanatory covariates (e.g. demographic and disease characteristics, co-morbidities, type of treating institution, and prior treatment for CHC and response outcome in treatment experienced patients) on SVR12. These analyses will be of exploratory nature, data driven, and will be performed for various CP analysis groups since not each covariate might be predictive in each patient group. Furthermore, the fact that treatment regimens will differ in the various patient groups has to be taken into account, when selecting the patient groups for each MLR analysis. Backward selection procedures will be applied to generate the final MLR models which will consider only covariates in the selection procedure with a p-value <0.25 in the corresponding univariate logistic regression analysis. A p-value <0.05 will be used for the covariates to stay in the model in a backward elimination step. Logistic regression methods will also be used to investigate the impact of treatment adherence on SVR12.

All safety variables will be summarized for patients in the SP using descriptive statistical methods stratified by the type of combination treatment and scheduled treatment duration.

Milestones:

Start of Data Collection:	Jan 2016
End of Data Collection:	Aug 2017
Final Report of Study Results:	May 2018

Confidential Information

No use or disclose outside AbbVie is permitted without prior written authorization from AbbVie

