The ABBVIE REGIMEN has been studied with and without RBV in over 2,300 patients in Phase III trials across a variety of patient populations including those with compensated cirrhosis. Based on Phase III data, the ABBVIE REGIMEN, with or without RBV, was well tolerated with a low discontinuation rate. Adverse events (AEs) were typically mild, and many of the AEs and laboratory abnormalities reported were attributable to the presence of RBV. However, these AEs were much milder than observed when RBV was given in combination with interferon. Transient, asymptomatic serum alanine aminotransferase (ALT) elevations were observed at a low rate, were not associated with hepatic dysfunction and generally resolved with ongoing treatment. A disproportionate number of the cases were in women on concurrent ethinyl estradiol-containing therapy (i.e., contraceptives or hormone replacement) and discontinuation of the hormonal therapy with continuation or brief interruption of the ABBVIE REGIMEN led to resolution in serum ALT elevation. Transient elevations in serum bilirubin (predominantly indirect) were observed in subjects receiving the ABBVIE REGIMEN with RBV, related to the inhibition of the bilirubin transporters, organic anion-transporting polypeptides (OATPs) 1B1/1B3, by paritaprevir and RBV-induced hemolysis. Bilirubin elevations occurred after initiation of treatment, peaked by study Week 1, and generally resolved with ongoing therapy. Bilirubin elevations were not associated with aminotransferase elevations. The frequency of indirect bilirubin elevations was lower among subjects who did not receive RBV.

Response of CHC genotype 4 was assessed in the phase II study PEARL-I in which 86 treatment-naïve patients were randomized to the 2 DAA combination of Paritaprevir/r – ombitasvir with vs. without RBV for 12 weeks. The SVR was 100% with RBV vs. 91% without RBV [61]. No serious SAEs or AEs leading to discontinuation were reported.

These results from pivotal studies are encouraging and the new interferon-free regimens might provide physicians with the armamentarium to cure the vast majority of patients

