9.4.1.2 During Treatment Documentation

Follow-up visits are scheduled by the physician per routine clinical practice. Likewise treatment, procedures and diagnostic methods will follow physicians' routine clinical practice.

The following will be documented:

- Laboratory data

Key clinical chemistry	Remarks
▪ ALT	including ULN
▪ AST	including ULN, APRI and FIB-4 will be calculated
▪ γ-GT	
▪ Total bilirubin	
▪ Creatinine	creatinine clearance will be calculated
Key hematology	
▪ Hb	
▪ Platelets	
Virology	
▪ HCV RNA	quantitative/ qualitative HCV RNA PCR test, see 9.4.1.4
HIV-infected patients only	
▪ CD 4 count	most recent assessment
▪ HIV RNA	in copies/mL

- Concomitant medication, see 9.4.1.5
- Adherence to ABBVIE REGIMEN ± RBV (ABBVIE REGIMEN - % of target dose taken and RBV Y/N)
- Tolerability (sAEs and AEs, see 11.5) and pregnancies (see 11.6)
- Patient questionnaires see 9.4.1.6
- PSP satisfaction and utilization questionnaires; PAM-13
- Treatment related health care resource utilization

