9.7.7 Tolerability Analysis

All tolerability variables will be summarized using descriptive statistical methods for the SP stratified by type of combination treatment and scheduled treatment duration.

All SAEs, non-serious AEs and pregnancy occurrences are to be reported for patients included in the study (see Section 11.0 and 9.2.3). AEs will be coded using MedDRA. The number and percentage of patients with treatment-emergent AEs (i.e. any reported event that begins or worsens in severity after initiation of study drug through 30 days post-study drug dosing) will be tabulated by primary MedDRA SOC and PT. Corresponding summary tables will be provided for all serious treatment-emergent AEs. The tabulation of the number of patients with treatment-emergent AEs by severity and relationship to study drug will also be provided. Patients reporting more than one AE for a given MedDRA PT will be counted only once for that term using the most severe incident for the severity summary table and the most related for the relationship summary table. Patients reporting more than one type of event within a SOC will be counted only once for that SOC.

Additional details of the analysis of AEs will be specified in the SAP.

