## 6 Analysis populations

*The target population (TP)* – all patients, who fulfill the following criteria:

- treatment-naïve or treatment-experienced adult (age at least 18 years) male or female patients with confirmed CHC with genotype 1 (1a and/or 1b) only, receiving combination therapy with the interferon-free ABBVIE REGIMEN  $\pm$  RBV according to standard of care and in line with the current local label. The prescribed ABBVIE REGIMEN needs to be known;
- if RBV is co-administered with the ABBVIE REGIMEN, it has been prescribed in line with the current local label (with special attention to contraception requirements and contraindication during pregnancy);
- patients with voluntarily signed and dated a patient authorization to use and/or disclosure his/her anonymized health data (or informed consent) prior to inclusion into the study;
- patients must not be participating or intending to participate in a concurrent interventional therapeutic study.

Patients who prematurely discontinue earlier than  $\leq$ study day 55 (for 12 weeks treatment) or  $\leq$ study day 139 (for 24 weeks treatment) will be used in analyses on the population with actual EoT time point without windowing conventions adjustment for EoT.

*The core population (CP)* – all patients of the TP, who have started the treatment combination recommended in the current local label for their disease characteristics. Patients, who fulfill at least one of the following conditions, will be excluded from the CP:

- patients with unknown fibrosis status;
- cirrhotic patients with genotype 1a not receiving ribavirin;
- patients with genotype 1 for whom two direct-acting antiviral agents regimen (2DAA) instead of 3DAA is prescribed;
- patients with EoT  $\leq$ study day 55 (for 12 weeks treatment) or  $\leq$ study day 139 (for 24 weeks treatment).

*The safety population (SP)* – all patients who received at least one dose of the ABBVIE REGIMEN.

 This table is based on the table 4 “Analysis time windows” of clinical study Protocol.

 These time windows are intended for the CP allocation filter only. In case of the TP, all patients will be used for the analysis regardless of actual EoT day relevance to EoT time windows.

 This section is based on the sections 9.7.1 “Analysis population, time windows and handling of missing data” and 9.2.1 “Target population” of clinical study Protocol.

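### SAP 11 splits the safety tables by scheduled, not received, ribavirin: any unscheduled recipient would be shown under -RBV, and any never-taker would dilute +RBV

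*SAP*

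**What the plan says.** SAP 11 covers exposure, adverse events, pregnancies and laboratory results in the safety population. It sets the columns in one sentence: "The results will be reported overall and for scheduled treatment combination" (± RBV) and duration. The shells for Tables 4.1 to 4.6 then head their columns with the regimen plus or minus RBV, and no as-received grouping is defined anywhere.

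SAP 6 defines the safety population as "all patients who received at least one dose of the ABBVIE REGIMEN", so membership depends on what was taken.

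Protocol 9.7.7 summarises tolerability "for the SP stratified by type of combination treatment and scheduled treatment duration", and the abstract (4.0) says "stratified by the type of combination treatment and scheduled treatment duration". In both places the word scheduled qualifies duration only. For the baseline tables, by contrast, Protocol 9.7.2 does refer to the scheduled combination.

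Protocol 9.4.1.2 lists as on-treatment adherence data "ABBVIE REGIMEN - % of target dose taken and RBV Y/N". SAP 16 declares the methods fully consistent with the protocol and names only the omitted PSP regression.

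**The concern.** Safety tables are normally read by what patients took. Ribavirin is the only drug component that SAP 11 uses to separate the regimen columns. The protocol's own background says of the phase III data that "many of the AEs and laboratory abnormalities reported were attributable to the presence of RBV", and it links ribavirin to haemolysis and bilirubin elevation. Describing the tolerability of the regimen with and without ribavirin is a secondary objective, so these columns carry that description.

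If the schedule and the intake differ for a patient, the column label no longer describes that patient's exposure. The planned outputs would not show how often this happens. No table cross-counts scheduled against received ribavirin, and SAP 8.2 says protocol deviations will not be presented.

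**Working it through.** **No planned figure depends on the grouping.** The study's only size calculation is the Clopper-Pearson interval for SVR12. With 158 × 0.90 = 142.2 responders it gives 84.23% to 94.20%, width 9.97 points, which agrees with the stated 84.2% to 94.2%. It is unaffected here; 158 is used below only as a scale.

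**Who is misplaced under the scheduled rule**

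| Scheduled | Taken | Column | Consequence |
|---|---|---|---|
| +RBV | full course | +RBV | correct |
| +RBV | reduced or stopped early | +RBV | correct: the patient was exposed |
| +RBV | never | +RBV | dilutes +RBV; no ribavirin harm to misplace |
| -RBV | never | -RBV | correct |
| -RBV | at least one dose | -RBV | ribavirin harms appear under -RBV |

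Only the last row puts ribavirin harms in the wrong column.

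**Size, on assumptions.** The documents give neither the number of discordant patients nor event rates by ribavirin use. Let p1 and p0 be the true event rates with and without ribavirin, a the share of scheduled +RBV patients who never take it, and b the share of scheduled -RBV patients who do take it. Then:

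- shown +RBV rate = (1 - a) × p1 + a × p0
- shown -RBV rate = (1 - b) × p0 + b × p1
- shown difference = (p1 - p0) × (1 - a - b)

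For a = b = m the difference is multiplied by 1 - 2m, that is 0.96, 0.90 and 0.80 at m = 2%, 5% and 10%.

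| Assumed p1 / p0 | m | Shown +RBV | Shown -RBV | Shown difference (true) |
|---|---|---|---|---|
| 20% / 5% | 2% | 19.70% | 5.30% | 14.4 (15.0) |
| 20% / 5% | 5% | 19.25% | 5.75% | 13.5 (15.0) |
| 20% / 5% | 10% | 18.50% | 6.50% | 12.0 (15.0) |
| 10% / 2% | 2% | 9.84% | 2.16% | 7.7 (8.0) |
| 10% / 2% | 5% | 9.60% | 2.40% | 7.2 (8.0) |
| 10% / 2% | 10% | 9.20% | 2.80% | 6.4 (8.0) |

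The two directions act on different columns. At 20% / 5%, a = 0 with b = 10% gives 20.0% against 6.5%. With a = 10% and b = 0 it gives 18.5% against 5.0%, so never-takers leave the -RBV rate unchanged.

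**In patients.** If 25% to 50% of 158 are scheduled for ribavirin, the -RBV column holds 118.5 to 79. The expected number of ribavirin-exposed patients with the event shown under -RBV is that number × b × p1. At p1 = 20% this is 0.3 to 0.5 patients for b = 2%, 0.8 to 1.2 for 5% and 1.6 to 2.4 for 10%. With no discordant patients it is zero.

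**The case against.** **Scheduled and received should mostly agree.** This is an observational study. The schedule is the physician's own prescription, made before enrolment, not a randomised assignment. No document shows a patient given unscheduled ribavirin. This stands, and it limits the point to a possible misplacement.

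**The conflict with the protocol is not established.** A reader might infer that the SAP contradicts the protocol. Protocol 9.7.7 speaks of type of combination treatment; it does not say received or as treated. SAP 2 also cites protocol version 4.0 of 11 July 2017, while the supplied protocol is version 3.0. The wording differs from version 3.0, but version 4.0 must be checked. The argument from how the safety population is defined does not depend on this.

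**The reason for collecting ribavirin Y/N is not given.** It is tempting to say that it is recorded because intake can depart from the plan. Protocol 9.4.1.2 lists it under adherence without a reason.

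**Other outputs help.** Tables 4.3.3 and 4.3.4 tabulate events by relationship to ribavirin, all adverse events are listed, and the overall columns are unaffected. This stands in part. Those two tables use the same columns, and the laboratory tables (4.5 and 4.6), where haemoglobin and bilirubin changes appear, carry no attribution.

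**The contrast is descriptive and already confounded,** because ribavirin use follows label and disease characteristics. True, but correct column labels matter for description too.

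**A received rule can misplace patients as well.** Only routinely available data are collected. If everyone without a recorded dose went to -RBV, exposed patients with no intake record would be misplaced. This stands, and the fix needs a rule for it.

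**Conclusion.** The point holds as a cheap improvement, not as a demonstrated error in the results. SAP 11 builds the safety columns from the scheduled ± RBV combination, although the population is defined by receipt and the supplied protocol attaches scheduled only to duration.

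A reader might infer that every deviation from the ribavirin schedule puts harms in the wrong column, or that the ribavirin-free regimen will look worse than it is. The documents do not support either. Reduced or shortened courses are correctly placed, never-takers affect only +RBV, and only unscheduled recipients would raise the -RBV rate.

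The number of such patients is unknown and may be zero. The shrinkage of 4% to 20% in the ± RBV difference rests entirely on assumed event rates and on an assumed discordance of 2% to 10%, equal in both directions.

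**What to change.** The change concerns analysis only:

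- In SAP 11, define the safety ± RBV group by ribavirin received: at least one recorded dose is +RBV; recorded as not taken is -RBV; intake not recorded keeps the scheduled group, with the count footnoted.
- Keep scheduled duration, and apply the rule to Tables 4.1 to 4.6.
- Footnote a scheduled-by-received cross-count.
- If a ribavirin start date is available, flag in the adverse event listing the events that began before ribavirin.
- Check the grouping against protocol version 4.0 and record any difference in SAP 16.

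Before programming, confirm which ribavirin intake fields exist. Protocol 9.4.1.2 mentions Y/N only and SAP 11.1 lists percentage of target dose only for the antivirals, yet the Table 4.1 shell shows that percentage for ribavirin.

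The cost is a few sentences and one derived variable from data already collected. Safety column Ns may differ slightly from the baseline columns (including those for the safety population) and from the effectiveness columns. Patients who add ribavirin mid-course bring some pre-ribavirin events into +RBV. If there is no discordance, the tables do not change and the footnote shows it.
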